APPENDIX 6. CLASSIFICATION OF RESCUE THERAPY

This appendix outlines the algorithm for the Arena clinical team/medical reviewers to classify rescue therapies for ulcerative colitis (UC) in a blinded manner. This will help establish 1) intercurrent events for the efficacy estimands, and 2) whether a subject will be excluded from the Per Protocol Set(s). All rescue therapies identified by the medical reviewers per the algorithm below will be imported in programming. This process will be repeated until database lock and the list of all rescue therapies identified will be finalized before study unblinding.

Only medications and medical procedures reported on the electronic case report forms (eCRFs) can be assessed whether they are rescue therapy for UC. If the exposure happens in the follow-up period (beginning on or after the date of last study treatment administration), then it would not be considered as a rescue therapy. Impact of rescue therapy use in the analysis is timing-dependent, eg, if a subject starts a rescue therapy between their Week 12 and Week 52 endpoint assessments, then it may have potential impact on Week 52 endpoint analysis but will have no impact on Week 12 endpoints. The rules outlined below apply to both new use and increase in dose from Baseline.

Biologics with immunomodulatory properties

- Rule:
 - Any exposure after first dose
- List of medications
 - Anti-TNFs:
 - ADALIMUMAB
 - CERTOLIZUMAB
 - CERTOLIZUMAB PEGOL
 - GOLIMUMAB
 - INFliximab
 - Other Biologics:
 - USTEKINUMAB
 - VEDOLIZUMAB

Non-biologics with immunomodulatory properties

- Immunosuppressants
 - Rule to consider for Week 12 efficacy endpoints:
 - After first dose and up to and including Week 8: any increase from baseline for more than 5 days

- After Week 8: Any dose above baseline
- Rule to consider for Week 52 efficacy endpoints:
 - After Week 12 and up to and including Week 40: any increase from baseline for more than 5 days
 - After Week 40: Any dose above baseline
- List of medications
 - MERCAPTOPURINE
 - AZATHIOPRINE
 - TIOGUANINE
 - METHOTREXATE
 - METHOTREXATE SODIUM
- 5-ASA COMPOUNDS
 - Rules to consider for Week 12 efficacy endpoints:
 - After first dose and up to and including Week 8: any increase from baseline for more than 5 days
 - After Week 8: Any dose above baseline
 - Rules to consider for Week 52 efficacy endpoints:
 - After Week 12 and up to and including Week 40: any increase from baseline for more than 5 days
 - After Week 40: Any dose above baseline
 - List of medications
 - MESALAZINE
 - BALSALAZIDE
 - BALSALAZIDE DISODIUM DIHYDRATE
 - BALSALAZIDE SODIUM
 - OLSALAZINE SODIUM
 - SULFASALAZINE
 - BECLOMETASONE W/MESALAZINE
 - Route
 - ORAL
 - RECTAL

- Other small molecule immunomodulatory active agents
 - Rule:
 - Any exposure after first dose
 - List of medications
 - CICLOSPORIN
 - TACROLIMUS
 - TOFACITINIB
 - TOFACITINIB CITRATE
- Systemic glucocorticoids
 - Systemic glucocorticoids given via oral or rectal routes of administration
 - Rule:
 - After first dose and up to and including Week 8: any increase from baseline for more than 7 days
 - After Week 8: Any dose above baseline
 - List of medications
 - BETAMETHASONE
 - BETAMETHASONE DIPROPIONATE
 - BETAMETHASONE SODIUM PHOSPHATE
 - DEXAMETHASONE
 - DEXAMETHASONE SODIUM PHOSPHATE
 - DEXAMETHASONE VALERATE
 - METHYLPREDNISOLONE
 - METHYLPREDNISOLONE SODIUM SUCCINATE
 - PREDNISOLONE
 - PREDNISOLONE SODIUM PHOSPHATE
 - PREDNISOLONE METASULFOBENZOATE SODIUM
 - PREDNISONE
 - TRIAMCINOLONE
 - HYDROCORTISONE
 - HYDROCORTISONE ACETATE

- HYDROCORTISONE BUTYRATE
- HYDROCORTISONE SODIUM SUCCINATE
- ROUTE
 - ORAL
 - RECTAL
- Systemic glucocorticoids given via parenteral routes of administration
 - Rule:
 - Any exposure after first dose
 - List of medications
 - BETAMETHASONE
 - BETAMETHASONE DIPROPIONATE
 - BETAMETHASONE SODIUM PHOSPHATE
 - DEXAMETHASONE
 - DEXAMETHASONE SODIUM PHOSPHATE
 - DEXAMETHASONE VALERATE
 - METHYLPPREDNISOLONE
 - METHYLPPREDNISOLONE SODIUM SUCCINATE
 - PREDNISOLONE
 - PREDNISOLONE SODIUM PHOSPHATE
 - PREDNISOLONE METASULFOBENZOATE SODIUM
 - PREDNISONE
 - TRIAMCINOLONE
 - HYDROCORTISONE
 - HYDROCORTISONE ACETATE
 - HYDROCORTISONE BUTYRATE
 - HYDROCORTISONE SODIUM SUCCINATE
 - ROUTE
 - INTRAVENOUS
 - INTRAMUSCULAR
- Topical Glucocorticoids

- Budesonide
 - Rule
 - Subjects not taking Budesonide at baseline:
 - After first dose and up to and including Week 8: more than 9 mg/day for one day or any exposure for more than 5 days
 - After Week 8: Any dose above baseline
 - Subjects taking Budesonide at baseline:
 - After first dose and up to and including Week 8: more than 9 mg/day for one day or any increase for more than 5 days
 - After Week 8: Any dose above baseline
 - List of medications
 - BUDESONIDE
 - List of Routes
 - ORAL
 - RECTAL
- Beclomethasone
 - Rule
 - Subjects not taking Beclomethasone at baseline:
 - After first dose and up to and including Week 8: more than 5 mg/day for one day OR any exposure for more than 5 days
 - After Week 8: Any dose above baseline
 - Subjects taking Beclomethasone at baseline:
 - After first dose and up to and including Week 8: more than 5 mg/day for one day or any increase for more than 5 days
 - After Week 8: Any dose above baseline
 - List of medications:
 - BECLOMETASONE
 - BECLOMETASONE DIPROPIONATE
 - BECLOMETASONE W/MESALAZINE
 - Routes:
 - ORAL
 - RECTAL

- Other small molecule immunomodulatory active agents
 - Rules to consider for Week 12 efficacy endpoints:
 - After first dose and up to and including Week 8: any increase from baseline (including new use) for more than 5 days
 - After Week 8: Any dose above baseline
 - Rules to consider for Week 52 efficacy endpoints:
 - After Week 12 and up to and including Week 40: any increase from baseline (including new use) for more than 5 days
 - After Week 40: Any dose above baseline
 - List of medications:
 - CICLOSPORIN
 - TACROLIMUS
 - TOFACITINIB
 - TOFACITINIB CITRATE
- Systemic glucocorticoids
 - Systemic glucocorticoids given via oral or rectal routes of administration
 - Rules to consider for Week 12 efficacy endpoints:
 - After first dose and up to and including Week 8: any increase from baseline for more than 7 days
 - After Week 8: Any dose above baseline
 - Rules to consider for Week 52 efficacy endpoints:
 - After Week 12 and up to and including Week 40: any increase from baseline for more than 7 days
 - After Week 40: Any dose above baseline
 - List of medications:
 - BETAMETHASONE
 - BETAMETHASONE DIPROPIONATE
 - BETAMETHASONE SODIUM PHOSPHATE
 - DEXAMETHASONE
 - DEXAMETHASONE SODIUM PHOSPHATE
 - DEXAMETHASONE VALERATE

- METHYLPREDNISOLONE
- METHYLPREDNISOLONE SODIUM SUCCINATE
- PREDNISOLONE
- PREDNISOLONE SODIUM PHOSPHATE
- PREDNISOLONE METASULFOBENZOATE SODIUM
- PREDNISONE
- TRIAMCINOLONE
- HYDROCORTISONE
- HYDROCORTISONE ACETATE
- HYDROCORTISONE BUTYRATE
- HYDROCORTISONE SODIUM SUCCINATE
- Routes:
 - ORAL
 - RECTAL
- Systemic glucocorticoids given via parenteral routes of administration
 - Rule for Week 12 endpoint:
 - Any exposure after first dose up to Week 12
 - Rules for Week 52 endpoint:
 - After Week 12 and up to and including Week 40: more than one dose
 - Any exposure after Week 40
 - List of medications:
 - BETAMETHASONE
 - BETAMETHASONE DIPROPIONATE
 - BETAMETHASONE SODIUM PHOSPHATE
 - DEXAMETHASONE
 - DEXAMETHASONE SODIUM PHOSPHATE
 - DEXAMETHASONE VALERATE
 - METHYLPREDNISOLONE
 - METHYLPREDNISOLONE SODIUM SUCCINATE
 - PREDNISOLONE

- PREDNISOLONE SODIUM PHOSPHATE
- PREDNISOLONE METASULFOBENZOATE SODIUM
- PREDNISONE
- TRIAMCINOLONE
- HYDROCORTISONE
- HYDROCORTISONE ACETATE
- HYDROCORTISONE BUTYRATE
- HYDROCORTISONE SODIUM SUCCINATE
- Routes:
 - INTRAVENOUS
 - INTRAMUSCULAR
- Topical Glucocorticoids
 - Rules for Week 12 endpoints:
 - After first dose and up to and including Week 8: any exposure above baseline (or new use) for more than 5 days
 - After Week 8: Any dose above baseline
 - Rules for Week 52 endpoints:
 - After Week 12 and up to and including Week 40: any increase from baseline for more than 5 days
 - After Week 40 any increase above baseline
 - List of medications:
 - BUDESONIDE
 - Routes:
 - ORAL
 - RECTAL
- Beclomethasone
 - Rules for Week 12 endpoints:
 - After first dose and up to and including Week 8: Any increase above baseline for more than 5 days
 - After Week 8: Any dose above baseline
 - Rules for Week 52 endpoints:

- After Week 12 and up to and including Week 40: Any increase from baseline for more than 5 days
- After Week 40 any increase above baseline
- List of medications:
 - BECLOMETASONE
 - BECLOMETASONE DIPROPIONATE
 - BECLOMETASONE W/MESALAZINE
- Routes:
 - ORAL
 - RECTAL

Medical procedures

- Leukocyte apheresis, other apheresis, and plasma exchange
 - Rule:
 - Any exposure after first dose
 - List of medical procedures
 - APHERESIS
 - LEUKAPHERESIS
 - COLECTOMY (partial or total)
 - SIGMOIDECTOMY
 - COLOSTOMY
 - ILEOSTOMY

Statistical Analysis Plan - non-PK part V1.0 - 28-Sep-2022

Electronic Signature Manifestation

This page is a manifestation of the electronic signature(s) used in compliance with the organization's electronic signature policies and procedures.

Signer Full Name	Meaning of Signature	Date and Time
PPD	Document Approval (I certify that I have the education, training and experience to perform this task)	27 Sep 2022 23:50:22 UTC
PPD	Document Approval (I certify that I have the education, training and experience to perform this task)	28 Sep 2022 00:04:48 UTC
PPD	Document Approval (I certify that I have the education, training and experience to perform this task)	28 Sep 2022 10:56:10 UTC

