Because transient fluctuations of ALT or AST are common, and progression to severe drug-induced liver injury or acute liver failure is uncommon, automatic discontinuation of study treatment upon finding a greater than 3 × ULN elevation of ALT or AST may be unnecessary.

Subjects who discontinue treatment prematurely, regardless of the reason, should be instructed to return for an Early Termination visit within 7 days of the last study treatment administration (Table 7) and before initiation of any new treatments to complete all of the early termination assessments. If a subject discontinues due to pregnancy, they are not required to complete the endoscopy. If the Early Termination visit is within 4 weeks of the last sigmoidoscopy and biopsy, these procedures do not need to be repeated.

If the Early Termination visit is ≥ 2 weeks of the last dose of study treatment, the 2-Week Follow-Up visit is not required; however, the 4-Week Follow-Up visit should be scheduled and completed. If the Early Termination visit is ≥ 4 weeks of the last dose of study treatment, the 4-Week Follow-Up visit is not required unless the absolute lymphocyte count (ALC) is not within normal limits.

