9.7.1.1. Endoscopy

A flexible proctosigmoidoscopy, performed with a video endoscope following cleansing preparation (oral or rectal cathartic), will be performed at the Week 52/Early Termination visit. Additional proctosigmoidoscopies may be performed to confirm disease worsening and are required for qualification into the OLE (Section 5.1.1).

To ensure quality data and standardization, the same endoscopist should be used throughout the study wherever possible. Endoscopy images will be obtained during each endoscopy and will be sent for central reading and determination of the Mayo endoscopic score. A detailed image review charter from the central reading laboratory will outline the endoscopic procedures, video

recordings, and equipment. For each subject, a video recording of the entire endoscopic procedure will be performed using an acceptable storage medium. The endoscopic recordings will be read centrally in a blinded manner for mucosal lesions and endoscopic severity by a qualified gastroenterologist according to the image review charter. The ES will be evaluated by the Investigator and the central reader. The central read will be used for determination of efficacy endpoints; however, treatment decisions will be made by the treating Investigator.

Repeated flexible proctosigmoidoscopy may be permitted by the Sponsor when the central reader indicates that the video endoscope data were acquired incorrectly or did not meet the minimal required quality standards.

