10.4. Missing Data

Subjects with worsening of disease, as defined in Section 5.1.1, will be considered as having a treatment nonresponse outcome in the analysis of all endpoints, including the primary endpoint.

In addition, subjects who initiate an agent not allowed in combination with the study treatment that can affect the efficacy of the study treatment, such as an immunosuppressant or corticosteroid, or who have an increase in dose over baseline levels for treatment of worsening disease symptoms will be considered non-responders thereafter or be handled by per protocol analysis.

Subjects discussed above will be considered as having a known outcome at the analysis timepoint (ie, a treatment failure outcome) and not as having missing data. Subjects who discontinue the double-blind study for reasons other than worsening disease or adverse event related to UC will be considered as having missing data and will be handled in the primary and sensitivity analyses as follows.

A full description of the handling of missing data will be provided in the SAP.

Primary Method of Handling Missing Data

In the primary analysis of the primary endpoint and main analyses of all binary responder-type endpoints, all subjects with missing data, regardless of reason for missingness, will be considered as non-responders.

In the main analysis of continuous or score endpoints, such as changes from baseline in MMS subscores, biomarker measures, urgency NRS, abdominal pain NRS, and health-related quality of life measures, subjects with missing data will be handled using last observation carry forward, or a mixed-effect model with repeated measures. Detailed methods will be provided in the SAP.

Sensitivity Analyses for Missing Data

Sensitivity analyses may be performed under several alternative assumptions regarding missing data, ie, data missing intermittently, after discontinuation from the double-blind study for reasons other than worsening diseases, or after initiation of excluded medications.

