2.5. Estimands

The primary and key secondary efficacy estimands to support regulatory decisions are described in Table 1. The analyses will be performed on the Full Analysis Set (FAS) as defined in Section 5.3. Other secondary efficacy variables (specified in Section 16.3.1) will have the population, intercurrent event handling strategy and population-level summary measure similar to the primary estimand. Supplementary analyses for the primary and the key secondary estimands will be performed on the modified Full Analysis Set (mFAS) and the Per Protocol populations, respectively .

Table 1 List of Primary and Key Secondary Estimands

Estimand	Definition	Attribute			
		Population	Variable/Endpoint	Intercurrent Event Handling Strategy	Population-Level Summary Measure
Primary Estimand 1	Efficacy of etrasimod on clinical remission at Week 52	Enrolled subjects who receive at least 1 dose of etrasimod	The proportion of subjects with SF = 0 (or = 1 with a \geq 1-point decrease from Baseline in APD334-302), RB = 0, and ES \leq 1 (excluding friability) at Week 52	Subjects with missing data for any reason (including discontinuation due to lack of efficacy or adverse event related to UC) or any of the 3 intercurrent events ^a before the efficacy assessment will be treated as nonresponders.	Difference between etrasimod and placebo in proportion of responders at Week 52
Key Secondary Estimand 1	Efficacy of etrasimod on endoscopic improvement at Week 52	Enrolled subjects who receive at least 1 dose of etrasimod	The proportion of subjects with ES of \leq 1 (excluding friability) at Week 52	Same as the intercurrent event handling strategy for the primary estimand	Difference between etrasimod and placebo in proportion of responders at Week 52
Key Secondary Estimand 2	Efficacy of etrasimod on symptomatic remission at Week 52	Enrolled subjects who receive at least 1 dose of etrasimod	The proportion of subjects with SF = 0 (or = 1 with a \geq 1-point decrease from Baseline in APD334-302) and RB = 0 at Week 52.	Same as the intercurrent event handling strategy for the primary estimand	Difference between etrasimod and placebo in proportion of responders at Week 52

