Key Secondary Estimand 3	Efficacy of etrasimod on corticosteroid-free clinical remission at Week 52	Enrolled subjects who receive at least 1 dose of etrasimod	The proportion of subjects with clinical remission at Week 52, while not receiving corticosteroids for 12 or more weeks in the 40-Week Treatment Period	Same as the intercurrent event handling strategy for the primary estimand	Difference between etrasimod and placebo in proportion of responders at Week 52
Key Secondary Estimand 4	Efficacy of etrasimod on mucosal healing at Week 52	Enrolled subjects who receive at least 1 dose of etrasimod	The proportion of subjects with ES of \leq 1 (excluding friability) with histologic remission measured by a Geboes Index score $<$ 2.0 at Week 52	Same as the intercurrent event handling strategy for the primary estimand	Difference between etrasimod and placebo in proportion of responders at Week 52

Estimand	Definition	Attribute			
		Population	Variable/Endpoint	Intercurrent Event Handling Strategy	Population-Level Summary Measure
Key Secondary Estimand 5	Efficacy of etrasimod on sustained clinical remission	Enrolled subjects who receive at least 1 dose of etrasimod	The proportion of subjects with sustained clinical remission (clinical remission at both Weeks 12 and 52)	Same as the intercurrent event handling strategy for the primary estimand	Difference between etrasimod and placebo in proportion of responders

^a Intercurrent events include: 1) initiate a rescue medication for UC, 2) have an increase in dose over Baseline levels in their existing UC medication, or 3) have colectomy or ileostomy before the efficacy assessment.

This SAP will analyze on the data collected in APD334-308 (from Week 16 to Week 52). The scope of analysis will be specified in Table/Listing/Figure shells. To fully address study primary objective “to assess the efficacy of etrasimod on clinical remission in Japanese subjects with moderately to severely active ulcerative colitis (UC) at timepoints up to 52 weeks of treatment (12 weeks in Study APD334-302 plus 40 weeks in Study APD334-308)”, after database lock and treatment unblinding, an integrated analysis of Study APD334-302 and Study APD334-308 will be performed for all Japanese subjects who had enrolled in ADP334-302 and covers the complete data from APD334-302 and to APD334-308.

3. STUDY Design

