16.1.2. Missing Data Methods for Primary Efficacy Variable

Subjects who 1) discontinue the study for lack of efficacy, or adverse event related to UC, 2) initiate a rescue medication for UC, 3) have an increase in dose over Baseline levels in their existing UC medication, or 4) have rescue medical procedure (e.g., colectomy, ileostomy, or sigmoidectomy) during the study as confirmed after blinded review by clinical and medical team members before study unblinding will be considered to have a known (i.e., non-missing) outcome of nonresponse in the analysis of all efficacy endpoints at any subsequent timepoints, including the primary endpoint. The rescue medications will be identified by the Arena clinical team during blinded data review. Refer to APPENDIX 6APPENDIX 6 for the definition of rescue therapies (medication and medical procedures). In scenarios #2 and #3 above, if a subject has efficacy measurement collected after the initiation or dose increase from Baseline of UC medication, the observed data will be censored at the time of initiation or dose increase and they will be considered having a nonresponse. Subjects in all 4 scenarios above may still be included in the respective Per Protocol Set, provided they do not violate other criteria for Per Protocol Set. For example, they will be excluded from the respective Per Protocol Set if they initiate a prohibited medication before Week 52 efficacy assessment that can affect efficacy of the study

treatment and the indication is unrelated to UC.

Analysis visits will be mapped as per Section 6.4 before any missing data imputation method is applied.

Subjects with missing efficacy outcome will be included in the primary analyses using single imputation as nonresponder. Supplementary analyses of efficacy outcomes will be performed in modified Full Analysis Set with data as observed.

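### SAP Appendix 6 stops counting rescue at the last study-drug dose, but the estimand counts it up to the efficacy assessment, so UC therapy begun between the two can leave a subject a Week 52 responder

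*SAP*

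**What the plan says.** - **SAP 2.5, Table 1** sets the strategy for the primary estimand, and the key secondary estimands adopt it. Subjects with missing data, or with one of three intercurrent events "before the efficacy assessment will be treated as nonresponders". Footnote a lists the events: starting a rescue medication for UC, raising the dose of an existing UC medication above Baseline, or to "have colectomy or ileostomy before the efficacy assessment".
- **SAP 16.1.2** repeats these nonresponse rules, adds discontinuation for lack of efficacy or a UC-related adverse event, and refers to Appendix 6 "for the definition of rescue therapies (medication and medical procedures").
- **SAP Appendix 6** states that its algorithm helps to establish the intercurrent events for the efficacy estimands. It then says: "If the exposure happens in the follow-up period (beginning on or after the date of last study treatment administration), then it would not be" treated as rescue. The next sentence makes the effect of rescue depend on timing, using the example "if a subject starts a rescue therapy between their Week 12 and Week 52 endpoint assessments".
- **Protocol 10.4** says that subjects who start a disallowed agent able to affect efficacy "will be considered non-responders thereafter or be handled by per protocol analysis". It gives no cut-off at the last dose.
- **SAP 6.4, Table 2** sets the Week 52 window for endoscopy and Mayo-based endpoints at Days 337 to 393, or to Day 421 if COVID-affected. Scheduled, unscheduled and Early Termination (ET) data can all be allocated to it.

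**The concern.** Appendix 6 is the text that medical reviewers apply to build the rescue list, and that list is then imported into the analysis programs. A therapy that Appendix 6 excludes is never flagged, so the 16.1.2 rule that censors data collected after rescue starts has nothing to act on. The intent was probably to ignore therapy begun once efficacy assessment is over. The rule is written as a last-dose date, however, and the last dose and the assessment need not fall together.

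Where they separate, an outcome reached on another UC therapy is credited to the randomised arm, contrary to the stated estimand. The same data also support two different responder lists, depending on which part of the SAP is followed. The point concerns newly started medication; Table 1 lists dose increases and colectomy or ileostomy as separate events.

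**Working it through.** The plan states no figure for this point, so the check compares the two rules and then works through the dates.

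**1. The two rules.** Let L be the last study-drug dose, S the start of a qualifying UC therapy, and A the assessment used for Week 52.

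| | Counts as rescue if |
|---|---|
| SAP Table 1 | S is before A |
| SAP Appendix 6 | S is before L |

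They disagree when S falls on or after L and before A. The Appendix 6 sentence about the period between the Week 12 and Week 52 assessments does not settle this. It speaks of rescue therapy, a class from which post-dose exposure has just been removed.

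**2. Can A fall after L and still supply the Week 52 result?** Yes, in three ways.
- *Repeat endoscopy.* Protocol 9.7.1.1: "Repeated flexible proctosigmoidoscopy may be permitted by the Sponsor when the central reader indicates that the video endoscope data were acquired incorrectly" or fell below quality standards. No deadline is stated, and dosing may have ended by then.
- *Late visit.* Protocol 5.1 asks for the ET visit within 7 days of the last dose and "before initiation of any new treatments to complete all of the early termination assessments". Protocol 9.5 nevertheless provides for ET or completion visits 2 weeks or more, and 4 weeks or more, after the last dose.
- *Unscheduled endoscopy* within Days 337 to 393 (421).

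**3. Date limits.**
- Compliant ET visit with last dose on or before Day 329: 329 + 7 = Day 336, which is before Day 337. There is no Week 52 value, so the subject is a nonresponder. Reaching the window from Day 329 needs 337 − 329 = 8 days or more.
- Completers: the protocol visit window ends at 365 + 7 = Day 372. The SAP window runs 393 − 372 = 21 days beyond that, or 421 − 372 = 49 days if COVID-affected. These are upper bounds on lateness, not expected gaps.

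**4. Example.** Last dose Day 345 for a reason unrelated to UC; new oral steroid Day 350; late ET endoscopy Day 366 with a centrally read score of 1. The ET visit is 366 − 345 = 21 days after the last dose, so this is a deviation, but Day 366 lies inside the window. Table 1 gives nonresponse for endoscopic improvement. Under Appendix 6 the steroid started after the last dose and is not rescue, so the subject is a responder.

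**5. Which endpoints are exposed.** Clinical and symptomatic remission also need diary scores from the preceding week (Protocol 9.4), and the diary runs through the treatment period (Protocol Table 7, note d). Where it stopped with dosing, those endpoints are missing and scored as nonresponse. Endoscopic improvement and mucosal healing need no diary, so they are the most exposed.

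**6. Weight of one subject.** About 35 subjects are planned, and the parent study randomised 2:1: 35 × 2/3 = 23.3 and 35 × 1/3 = 11.7, taken as 23:12. SAP 6.5 notes that allocation within Japan was not controlled, so a range of assumed splits is shown.

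| Assumed split | Etrasimod, 1/n | Placebo, 1/n |
|---|---|---|
| 20:15 | 5.0 points | 6.7 points |
| 23:12 | 4.3 points | 8.3 points |
| 26:9 | 3.8 points | 11.1 points |

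**7. Illustration with invented responder counts (23:12, Fisher's exact test).**

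| Counts | Difference | Nominal p |
|---|---|---|
| 9/23 v 1/12 | 30.8 points | 0.113 |
| one etrasimod responder fewer, 8/23 v 1/12 | 26.4 points | 0.121 |
| one placebo responder fewer, 9/23 v 0/12 | 39.1 points | 0.015 |
| 8/23 v 2/12 | 18.1 points | 0.434 |
| one etrasimod responder fewer, 7/23 v 2/12 | 13.8 points | 0.450 |
| one placebo responder fewer, 8/23 v 1/12 | 26.4 points | 0.121 |

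The shift can favour either arm, and its size depends on counts that the documents do not give.

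**The case against.** The strongest reply is that this is a wording slip with almost no reach.

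- For ordinary completers the two dates nearly coincide, because the visit-day dose is taken on site after the assessments. The 2- and 4-week follow-up visits are kept out of the analysis windows.
- A compliant ET visit precedes any new treatment. Stopping for lack of efficacy or a UC-related adverse event is nonresponse anyway, and so is missing data.
- Unscheduled endoscopies are mostly done to confirm worsening, and entry to the open-label study on that ground needs an endoscopic score of at least 2, so those subjects rarely respond. When several results share a window, the one nearest the scheduled day is used.
- Rescue is adjudicated by blinded reviewers, not by an automatic date rule.
- Protocol 10.4 can be read as presupposing ongoing study treatment, and it leaves detail to the SAP.
- The percentage-point figures are simply 1/n and would apply to any reclassified subject.

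Most of this stands as a limit on frequency. It does not remove the conflict. Late ET or completion visits and repeat endoscopies are not follow-up visits and still map to Week 52. An unusable first video leaves no earlier score to take precedence. The reviewers are instructed to apply Appendix 6, so adjudication carries its cut-off forward. The reading of Protocol 10.4 is open to argument, but the conflict between Table 1 and Appendix 6 does not depend on it.

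**Conclusion.** The concern holds. The SAP gives two cut-offs for the same intercurrent event, and the one in the operational appendix departs from the stated estimand. The reach is narrow. A subject must start UC therapy on or after the last dose and before the assessment used for Week 52, must not have stopped for lack of efficacy or a UC-related adverse event, and must meet the endpoint. The number of such subjects cannot be derived from the documents and is likely to be small.

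The per-subject effects in the working rest on the planned total and on assumed splits. With no formal efficacy test, what is affected is the reported percentages, differences and nominal p-values. In a study of this size, one subject is visible in those results. The contradiction is certain and cheap to remove, so it should be fixed even though it will seldom matter.

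**What to change.** Replace the last-dose sentence in SAP Appendix 6 with:

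> For each analysis visit, a therapy or procedure that meets the rules below counts as rescue if it begins before the efficacy assessment used for that visit, whether or not study treatment has stopped. Exposure beginning after that assessment does not affect that visit. Where only dates are recorded, a start on the same day counts as after the assessment.

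This still ignores therapy begun once assessment is over, and it brings Appendix 6 into line with Table 1, including the procedures in footnote a. The same-day rule is a convention; it fits the instruction that ET assessments precede new treatment.

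The cost is one sentence and one date comparison, using medication, procedure and assessment dates already collected, with the blinded rescue list rechecked before unblinding. The downside is that a few subjects may move from responder to nonresponder.
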